List your research objectives and hypotheses.

We hypothesize that intra-operative, intravenous secretin administration will decrease the rate of pancreatic leaks in patients undergoing pancreatic resection. Our primary objective is to determine if intravenous secretin administration will decrease the amount of pancreatic leaks as defined by the 2016 ISGPS definition of postoperative pancreatic fistula, measured by drain fluid amylase on or after POD#3days following resection. Our secondary objectives are to determine if intra-operative intravenous secretin administration changes the management of the pancreatic resection margin intraoperatively or impacts length of stay (LOS)

3. Introduction:

a) Explain the background of this project so that we will understand why it is important to perform this research project. b) Summarize previously published data and pilot studies. Be sure to include a discussion of any data that do not support the study hypothesis. If a study similar to the one being

proposed has already been completed, explain why the proposed study is necessary. c) For studies designed to compare or evaluate therapies, there should be a statement of the relative advantages or disadvantages of alternative modes of therapy. d) If not obvious, explain why human subjects are necessary. Include references for all published data cited. If a formal protocol for the study exists, page references to the protocol are acceptable.

A) Pancreatic duct leaks represent a major complication of pancreatic resection surgery. With a rate of between 20% even at expert, high-volume centers, this dreaded complication causes significant morbidity for patients with associated increased hospital costs. Treatment of pancreatic duct leaks often requires pancreatic rest with intravenous nutrition, endoscopic placement of pancreatic duct stents, and/or repeat surgical operation to close the leak. Despite many advancements in terms of leak closure techniques (duct to mucosa pancreaticojejunostomy, roux-en-Y reconstruction, devices (automatic staplers/ pledgets/stents) pancreatic leaks continue to be a major problem and pancreatic surgeons continue to search for methods to prevent or diminish the severity of pancreatic leaks.

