10 minutes after receiving the Secretin or placebo, the attending surgeon will examine the anastomosis or repaired cut edge of the pancreas to determine if leakage of pancreatic fluid is noted, leak location(s), type (side branch/main duct), color of the fluid and whether any further intervention was performed in an effort to close the leak. Specifics of operative intervention will be documented. The patient will then undergo standard surgical closure of the abdomen.

As is standard of care at DHMC, surgical drains will be placed adjacent to the anastomosis and drain amylase output will be checked on POD #1 through POD#5. Pancreatic leak is defined according to the International Study Group of Pancreatic Fistula (ISGPF) definition as a clinically relevant postoperative pancreatic fistula is now redefined as a drain output of any measurable volume of fluid with an amylase level >3 times the upper limit of institutional normal serum amylase activity, associated with a clinically relevant development/condition related directly to the postoperative pancreatic fistula. Randomization assignments will be revealed once the patient has been discharged from the hospital following their initial surgical intervention. A follow-up visit with the patient two weeks following discharge, will evaluate for any evidence of ongoing pancreatic duct leak.

The patient will also be followed for thirty (30) days after secretin/placebo administration by the research team to assess for a pancreatic leak and sequelae of a leak, - intra abdominal deep soft tissue infection, surgical site infection, hemorrhage, IR (interventional radiology) drain placement, or reoperation. This will be accomplished by telephone and/or by chart review Patients discharge date will be followed for the study. If no secretin/placebo is administered, the patient will not be followed on the study.

If any of the above are noted during the 30 days following secretin/placebo administration the following will be used to assess causality:

Causality

The following 4-point scale will be used for rating the causal relationship of the AE to the investigational product:

Unrelated: Clearly and incontrovertibly due to extraneous causes, and does not meet criteria listed under unlikely, possible, or probable.

- Unlikely:** Does not follow a reasonable temporal sequence from administration. May have been produced by the patient's clinical state or by environmental factors or other therapies administered.

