- Possible:** Follows as reasonable temporal sequence from administration. May have been produced by the patient's clinical state or by environmental factors or other therapies administered.
- Probable:** Clear-cut temporal association with improvement or cessation of test drug or reduction in dose. Reappears upon re-challenge. Follows a known pattern or response to test drug.

The primary outcome of interest will be the presence of pancreatic leaks based on the amount of drain amylase on or after POD#3. Secondary outcomes will include: 1) technical interventions intraoperatively directed to leak closure or manipulation of the anastomosis following Secretin or placebo stimulation 2) length of stay as a surrogate to complication severity after pancreatic surgery.

Patient demographics, risk factors, operative technique, randomization assignment and outcome data will be recorded on standard case report forms – **See Case Report Forms in Appendix**. Data will be stored in an encrypted hard-drive by a single agent ([name]) who is the only researcher who has access to the randomization data.

5. Inclusion/Exclusion Criteria:

Please provide detailed description of inclusion and exclusion criteria. If a formal protocol for the study exists, page references to the protocol are acceptable.

Inclusion criteria:

1. Scheduled for pancreatic surgery requiring pancreatic resection at DHMC
2. Age greater than 18 years old
3. Ability to provide written informed consent

Exclusion criteria:

1. Inability to provide written informed consent
2. Current ongoing acute pancreatitis
3. Pregnant or nursing mothers
4. Any medical condition which in the judgment of the Investigator renders participation in this study medically inadvisable.
5. Participation in an investigational clinical study for a drug or medical device within 30 days prior to Visit 1.
6. [Any known allergy to methylene blue.](#)

6. Financial Considerations:

Disclosure of financial impact on the participant is critical to informed consent. Insurance cannot be billed for research-related services outside the standard of care or paid for by the funding agency for

the study. The department, the study or the participant may be responsible for payment for research-related services. Participants should know which tests, visits, or procedures will be billed to them or their insurance and which ones will be paid by the funding agency for the study or the department.

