a) *List tests, visits, and procedures performed for only research purposes. These services are outside the standard of care. They would not be performed if the individual were not a research participant, and may not be billed to a health insurance plan.*

Note: 6a information must also be in "How is this different . . ." section of the consent form.

The administration of Secretin or placebo is for research purposes only and will not be billed to the patient. Drain placement, drain amylase measurement and the two week follow-up visit are per standard of care and will be billed directly to the patient.

b) *List the tests, visits, and procedures that may be standard care, but for which the funding agency for the study is paying.*

None

c) *Will the funding agency for the study be responsible for the above costs? Yes No
If No, describe who will be responsible (i.e., department or participant).*

Secretin will be supplied by ChiRhoClin, Inc and saline placebo will be supplied by the Section of Gastroenterology and Hepatology out of research funds maintained by the primary investigators. No additional tests, visits, or procedures will be performed for research purposes only.

PLEASE ENCLOSE THE DHMC BILLING GRID/PLAN. Also enclose the schedule of events or table listing all procedures from the sponsor protocol.

7. Statistical Methods and Review Statement:

a) *Specify the primary endpoint, as well as other endpoint(s).*

Primary Objective:

1. Pancreatic leak as defined by the ISGPF definition of post-operative pancreatic leaks

Secondary Objective:

1. Assess whether intervention is performed intra-operatively on the pancreatic anastomosis following Secretin or placebo injection.
2. Assess degree to which leakage severity, as a complication, increases length of stay.

b) *State the statistical analysis plan, including all hypothesis tests (e.g., t-test, chi-square), and estimation methods related to the primary endpoint. If a formal protocol for the study exists, page references to the protocol are acceptable.*

For the analysis of the primary endpoint, a categorical variable, we will use a two-tailed Fisher's Exact test to determine a p-value. We will then be able to calculate an absolute and relative risk reduction. We will also evaluate this variable using a student's t-test for means of amylase levels in the drain fluid. We will plan on performing univariate analysis of all of the potentially contributing variables outlined in the

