CRF, and then building a multivariable logistic regression model using the categorical variable of drain amylase >3x the upper limit of normal. The data from the multivariate regression will be reported as Odds Ratios.

The secondary outcomes are both categorical and continuous variables and thus we will use the Fisher's Exact test as well as the two-tailed student's t-test. A multivariable analysis is not planned for evaluating the secondary variable.

Randomization will occur in a block format of 5 and will be generated by the primary investigators.

c) Justify the sample size, using the concepts of power, type I error, and effect size if applicable. If a formal protocol for the study exists, page references to the protocol are acceptable.

A clinically significant absolute decrease of 15% (20% to 5%) in the pancreatic duct leak rate. Based on these estimates and a two-tailed test comparing proportions using the statistical calculator (<http://homepage.stat.uiowa.edu/~rlenth/Power>), we project an estimated sample size of **176 participants (88 per arm)** to demonstrate an absolute 15% reduction in the leak rate with 80% power at a two-sided alpha level of 0.05.

8. Data and Safety Monitoring:

Describe plans for data and safety monitoring to ensure the safety of subjects and the quality of the data. As described in federal guidance "... a variety of types of monitoring may be anticipated depending on the nature, size, and complexity of the trial. In many cases, the principal investigator would be expected to perform the monitoring function." This plan should include monitoring to determine:

The progress of the trial, including periodic assessments of data quality and timeliness, participant recruitment, accrual and retention, participant risk versus benefit, and other factors that can affect study outcome. Monitoring should also consider factors external to the study when interpreting the data, such as scientific or therapeutic developments that may have an impact on the safety of the participants or the ethics of the study.

Note: This section does not request information related to sponsor study monitor visits. This section requires a description of an adequate data and safety monitoring plan.

Interim analysis will be performed once 50% (88) patients have been enrolled. If more than 66% of cases of duct leak are in a particular study group, a formal comparison between groups will be performed with the use of a two-sided stopping boundary of 0.005%.

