Attachment B
Placebo or Procedures that are Inconsistent with the Standard of Care

Consider the ethical implications of using a placebo or procedures that are inconsistent with the standard of care in this study. Specifically, explain what "standard of care" therapy is for this participant population and how the use of placebo therapy may affect risks for participants. Also discuss:

- a) the safety and efficacy of other available therapies (if any),*
- b) the maximum total length of time a participant may receive placebo on study,*
- c) the greatest potential harm that may come to a participant as a result of not receiving effective therapy (immediate or delayed onset), and*
- d) safeguards for the participants receiving placebo.*

Required comment from the local research team specifically addressing a-d above and in addition to any justification included in the study protocol. Information copied directly from the protocol is not acceptable in this section:

At this time, in average risk patients, we are unclear of giving Secretin intra-operatively will allow better identification and repair of pancreatic duct leaks. The drug is used occasionally in high risk patients to evaluate for duct leaks and we would like to see if this drug is universally useful in all patients undergoing pancreatic surgery. The patient will only be included in the study from the time of their surgery to initial hospital discharge. The risk of not receiving therapy is that they may have a higher risk of duct leak (we will know better after the study). Patients receiving placebo will receive the same standard of care post-operatively than those receiving Secretin stimulation.

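### Length of stay is undefined and has no rule for death or readmission, so some of the worst outcomes count as short stays and the difference between arms is likely to be diluted

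*Combined protocol and SAP*

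**What the plan says.** Section 4 (Design, procedures, materials and methods) names the second secondary outcome as "length of stay as a surrogate to complication severity after pancreatic surgery". The same section gives the only datum for it: "Patients discharge date will be followed for the study". No start point, end point, or treatment of death or readmission is stated.

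Three places suggest that the first discharge is meant. Section 4 reveals the assignment when the patient leaves hospital after the initial operation. Section 13a describes participation as running through discharge after surgery, followed by a clinic visit. Attachment B says "The patient will only be included in the study from the time of their surgery to initial hospital discharge".

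For the secondary outcomes Section 7b says "we will use the Fisher's Exact test as well as the two-tailed student's t-test". Length of stay is the continuous one, so it gets the t-test.

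Section 4 also provides longer surveillance: "The patient will also be followed for thirty (30) days after secretin/placebo administration by the research team", by telephone or chart review. The events listed are leak, two kinds of infection, and "hemorrhage, IR (interventional radiology) drain placement, or reoperation". Death and readmission are not on the list.

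The question itself is worded in more than one way. Section 2 asks whether secretin affects stay. Section 7a instead says "Assess degree to which leakage severity, as a complication, increases length of stay", which is an association with leak severity, not a comparison of arms.

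**The concern.** A surrogate for severity should rank a worse course as worse. Index stay does so for a leak treated before the patient goes home. It fails for two kinds of patient. One who dies early in hospital has a short stay. One who goes home early and comes back with a complication keeps the short first stay, and the readmission days are not counted.

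This matters because the hypothesis in Section 3 covers the severity of leaks as well as their incidence. The primary endpoint is presence or absence of a leak, and the other secondary endpoint is what the surgeon did in theatre. Length of stay is the only listed endpoint offered as a measure of severity. The 30-day events are collected and rated for causality, but Section 7 names no analysis that would bring them into the severity comparison.

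**Working it through.** **The plan's own figure.** No mean, standard deviation or effect is given for length of stay. The only sample size figure is 88 per arm (176 in total) for leak rates of 20% and 5%, with two-sided alpha 0.05 and 80% power (Section 7c).

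- Without continuity correction: n = [1.960 × √(2 × 0.125 × 0.875) + 0.8416 × √(0.20 × 0.80 + 0.05 × 0.95)]² / 0.15² = 75.1, so 76 per arm.
- With continuity correction: (75.1/4) × [1 + √(1 + 4/(75.1 × 0.15))]² = 87.9, so 88 per arm.

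The stated 176 reproduces with the correction. Length of stay does not enter it.

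**What the scoring rule does.** The documents give no death rate, readmission rate or length of stay, so every stay and every share below is an assumption for illustration. Only the leak rates come from the plan.

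- No leak: 8 days.
- Leak managed in the index stay: 16 days.
- Leak with early in-hospital death: 5 days.
- Leak with early discharge and readmission: 6 index days plus 10 readmission days.
- A share d of leaks ends in early death and a share r in early discharge with readmission, the same in both arms.

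Mean index stay among leaks = 16(1 − d − r) + 5d + 6r. The difference between arms (placebo minus secretin) = (0.20 − 0.05) × (mean among leaks − 8).

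For comparison, the last two columns count readmission days and score a death as 30 days: mean among leaks = 16(1 − d) + 30d.

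| d | r | Index: mean in leaks | Index: difference | Day-30 total: mean in leaks | Day-30 total: difference |
|---|---|---|---|---|---|
| 0 | 0 | 16.00 | 1.20 | 16.0 | 1.20 |
| 5% | 25% | 12.95 | 0.7425 | 16.7 | 1.305 |
| 10% | 30% | 11.90 | 0.585 | 17.4 | 1.41 |
| 10% | 50% | 9.90 | 0.285 | 17.4 | 1.41 |
| 20% | 60% | 7.80 | −0.03 | 18.8 | 1.62 |

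**Individual patients.** The early death (5 days) and the early discharge with readmission (6 days) both score below the patient with no leak (8 days). For them the order is inverted.

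**The arm comparison.** It reverses only when the mean index stay among leaks falls below 8 days. If all the short stays are readmissions, 16 − 10r = 8 gives r = 80%. If all are early deaths, 16 − 11d = 8 gives d = 73%. Below that range the effect is diluted, not reversed.

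**The case against.** The strongest reply is that the documents leave length of stay undefined; they do not define it wrongly. The sentence about the discharge date does not say which discharge. The statement in Attachment B concerns participation and conflicts with the 30-day follow-up in Section 4. The case report form, which might hold a definition, is not in the supplied text. This stands in part: index stay is an inference, though three places support it. If the form does define the outcome, the definition still belongs in the analysis plan.

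A reader might infer that length of stay runs the wrong way for the worst leaks in general. The documents do not support that. Section 1 describes treatment with parenteral nutrition, drains, stents and, in severe cases, reoperation. Given during the index admission, these would be expected to lengthen the stay. A death after a long stay also scores long.

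A reader might also expect the arm comparison to reverse. With the same mix in both arms that takes an extreme share of leaks. A reversal caused by unequal deaths between arms is possible in principle, but the documents give no mortality figure from which to judge it.

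Nor can a percentage loss be quoted. Assuming that some share of leaks adds no index days, and then reporting that share of the effect as lost, only restates the assumption. The two-week visit does not supply the share either, because it looks for an ongoing leak, which is persistence, not first appearance.

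It can also be said that the endpoint is weak whatever the definition. With an assumed standard deviation of 5 to 8 days, 88 per arm gives about 10% to 36% power for a true difference of 0.75 to 1.2 days (0.15 × an assumed 5 to 8 extra days per leak). This stands as a reason to keep the point in proportion. It does not justify an estimate that misses part of what it is meant to measure.

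Finally, index stay has one real advantage. Assignments are revealed at the initial discharge, so index stay accrues wholly under blinding. Readmission is discretionary and would come after unblinding. The fix must deal with this.

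**Conclusion.** The point holds in a limited form. Length of stay is undefined, appears to be index stay, and has no rule for death or readmission. Following the plan as written scores an early in-hospital death, or an early discharge with later readmission, as a short stay on the only endpoint put forward for severity. Severe leaks managed during the index stay are scored in the right direction.

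The likely consequence is a difference between arms that is too small. Its size cannot be derived from the documents. The illustration shows only the direction and that moderate shares are enough to matter, and it rests entirely on assumed stays and on the same mix in both arms. The primary endpoint and the sample size are untouched. It is worth correcting because the change is cheap and because a rule chosen after unblinded data exist would be open to selection.

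**What to change.** In Section 7, define the outcome as total hospital days from surgery to day 30, including readmission days. Give any death by day 30 the worst rank, and compare the arms with a rank-sum test. State that the question is the effect of secretin on this outcome, and reconcile Section 7a with Section 2. Report index stay alongside, as the measure accrued wholly under blinding.

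In Section 4, add dates of death, readmission and later discharge to the 30-day telephone and chart review. Keep the assignment concealed until day 30 instead of revealing it at the initial discharge, so that readmission days are not open to bias from knowledge of the arm.

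The costs are a few added data items, later unblinding, stays capped at day 30, and reliance on telephone contact for readmissions to other hospitals. No extra patients or visits are needed.

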C) This would be a randomized, double-blind, placebo controlled trial. 1/2 of the patients would receive intra-operative secretin, the other half would receive saline placebo. Both the surgeon and patient would be blinded to the randomization assignment. The advantage of giving secretin would be that it may allow for the identification of a leak intra-operatively and subsequently allow for repair if the leak was identified prior to abdominal wall closure. While the safety profile of the drug is excellent, receiving the medication could theoretically cause an increased intraductal pressure which may cause a leak when one was not already present.

D) Human subjects are needed to evaluate intra-operative, intravenous secretin in patients undergoing pancreatic duct resection.

4. Design, procedures, materials and methods:

Use a level of detail similar to what would be used when submitting an article for publication in a peer reviewed journal. Explain the study procedures, data collection, and analysis process. Please define terms and explain concepts which might be confusing to reviewers who are not expert in the area of the study. If a formal protocol for the study exists, page references to the protocol are acceptable.

This study design is a prospective, double-blind, randomized-controlled trial. We will enroll patients in our institution undergoing pancreatic resection to receive either 1) one dose weight-based Secretin to be given once the closure of the pancreatic resection margin is complete 2) saline placebo.

Consent and basic demographics will be garnered by the physician in an office visit once the surgery has been scheduled and consent for the surgery is being obtained. The consent will be validated by the treating surgeon in the pre-procedure area on the day of the surgery.

The patient will undergo the scheduled surgery. Once the pancreatic anastomosis has been deemed acceptable by the attending physician, but prior to abdominal closure, the patient will be randomized to receive either Secretin (0.2 mcg/kg) or saline placebo. The attending surgeon will be blinded to this assignment.

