Synthetic secretin is FDA approved to diagnose exocrine pancreas dysfunction by the functional secretin stimulated pancreas function test and to facilitate pancreatic duct cannulation during ERCP. It is identical in amino acid sequence to native human secretin.

There has not been any reported adverse drug reaction to human secretin stimulation. Rarely, in over 1000 patients who have undergone Secretin-enhanced pancreatic function tests, there is transient vasodilatory effect resulting in flushing of the face and lips with stable vital signs. Therefore, the risks of administering intravenous secretin are modest as described in the package label.

In doses (800cu SQ bid x 7 days) given in clinical studies greater than those offered in the current study, there were no adverse events reported

Secretin is not known to increase the risk of acute pancreatitis episodes in patients with chronic pancreatitis not presently having an acute pancreatitis attack. No allergic reactions have been reported with secretin in commercial use although the administration of a test dose 0.2 mcg IV is still recommended. No significant hemodynamic effects have been observed following administration of secretin. Otherwise, the risks of administering secretin are modest as described in the package label.

The risk of confidentiality should be low given the case report form will be only available to [name] and will be kept in a locked cabinet. All data will be entered on a password-protected Microsoft Excel spreadsheet. Any statistical analysis will be done with patient study numbers and initials for identification of patient.

15. Risk/Benefit analysis:

Describe why the risks to subjects are reasonable in relation to the anticipated benefits to participants and in relation to the importance of the knowledge that may reasonably be expected to result from the study.

A potential risk reduction of up to 15% for pancreatic duct leaks outweighs the given theoretical risks of one time Secretin administration.

16. Research Setting

a) Is this a multi-center study?

Yes No

If yes: Are you the lead investigator? Yes No *If*

you are NOT the lead investigator:

Name of lead investigator:

Institution where the lead investigator is located:

b) List all sites where research will take place and the CPHS at Dartmouth College is the reviewing IRB (e.g. DHMC Alliance Hospitals, DHMC Clinics, WRJ VAMC):

Dartmouth-Hitchcock Medical Center

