If yes, please identify the activities and describe the plan to protect the privacy of participants. For example, a plan for protection of privacy might consist of conducting the assent process for an adolescent minor in a private setting, rather than in the presence of the minor's parent.

b) *Will the data collected in the course of the study be considered sensitive, e.g., include information about a mental health disorder, HIV status, or SS#?* Yes No

If yes, provide the rationale for why these data are needed:

If yes, could any of these data, if disclosed, damage financial standing, employability, insurability, or reputation?

Yes No

If yes, will a Certificate of Confidentiality be obtained? Yes No

Any person engaged in research collecting information about illegal conduct from human research subjects may apply for a Certificate of Confidentiality. NIH provides detailed instructions for investigators wishing to make an application at <http://grants.nih.gov/grants/policy/coc/index.htm>.

c) *Describe specific physical, administrative, and technical safeguards employed to secure data, e.g., limitation of access to data, use of locked file cabinets, protection of computer-based data systems. Data will be kept by one investigator ([name]) on a password-protected hard drive that only he has access to. No other investigators will have access to this data.*

d) *Will data that identify individual subjects be published or in any way be disclosed to third parties other than project personnel?*

Yes No

If yes, please explain here and incorporate the information in consent form:

28. Responsibility for costs of injury or illness related to research:

Will the sponsor or other funding agency be responsible for costs of injury or illness related to the research?

Yes No

If applicable, describe whether or not the sponsor will be responsible for investigational device removal if required:

If the sponsor or other funding agency will not be responsible for costs of injury or illness related to research, please complete:

a) *The reasons why the sponsor or funding agency is not accepting responsibility for research-related injury.*

All procedures for Secretin stimulation are standard of care

b) *Summary of risks as related to potential costs that could be incurred as a result of research-related injury or illness.*

The risk of using one dose of Secretin are extremely rare. Please see above.

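### Treatment arm and outcomes share the case report forms and one custodian, and nothing in the plan keeps a person who knows the arm from classifying leaks

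*Combined protocol and SAP*

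**What the plan says.** Section 4 lists what the forms will contain: "operative technique, randomization assignment and outcome data will be recorded on standard case report forms". The data are stored by a single agent, "who is the only researcher who has access to the randomization data". Section 14b adds that "the case report form will be only available to [name] and will be kept in a locked cabinet". Section 27c keeps the data with one investigator and states: "No other investigators will have access to this data".

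On blinding, Section 3C says: "Both the surgeon and patient would be blinded to the randomization assignment". No data collector, outcome assessor or adjudicator is described as blinded. Section 7b has the primary investigators, in the plural, generate the randomization.

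On timing, Section 4 says: "Randomization assignments will be revealed once the patient has been discharged from the hospital following their initial surgical intervention". A clinic visit two weeks after discharge then looks for continuing leak. Section 4 also says: "The patient will also be followed for thirty (30) days after secretin/placebo administration by the research team to assess for a pancreatic leak". That follow-up is by telephone, chart review or both.

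On the outcome, one part of Section 4 describes the primary outcome as "the presence of pancreatic leaks based on the amount of drain amylase on or after POD#3". Another part gives the ISGPF definition, which requires the raised amylase together with a clinically relevant condition attributed to the fistula. Section 7a makes the ISGPF definition the primary endpoint.

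**The concern.** Blinding the surgeon and the patient protects the operation and the patient's own reports. It does not protect the step at which someone decides whether a patient had a leak. That protection needs the person making the decision not to know the arm, and the plan never provides for it. Instead it places arm and outcome on the same forms, in the custody of a researcher whose access to the randomization data has no stated start or end.

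An amylase result is hard to bias. Whether a collection, infection or bleed was caused by the fistula is a judgement. If it is made by someone who knows the arm and favours the hypothesis, secretin-arm leaks may be called less often, or placebo-arm leaks more often. Leaks are few, so a small number of such calls could move the primary comparison.

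**Working it through.** **1. Who can know the arm, and when**

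| Question | What the text gives | What it leaves open |
|---|---|---|
| Where is the arm recorded? | On the forms, with the outcomes (Section 4) | When it is entered |
| Who holds it? | One researcher, who also stores the data (Section 4) | Whether that person completes forms or classifies leaks |
| Who generated it? | The primary investigators (Section 7b) | How this fits with a single holder |
| Who is blinded? | Surgeon and patient (Section 3C) | Everyone else |
| When is it released? | At discharge (Section 4) | To whom |
| Who looks for leaks after release? | The clinic visit and the research team to day 30 (Section 4) | Whether they know the arm, and whether these findings count in the primary endpoint |

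Names are removed from the text, so it is an inference that Sections 4, 14b and 27c mean the same person. Section 4 alone establishes that one person holds both arm and outcomes.

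**2. The plan's own figure**

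Inputs from Section 7c: 20% v 5%, two-sided alpha 0.05, power 80%. The pooled rate is 0.125 and the difference is 0.15.

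- Without continuity correction: n = [1.960 × √(2 × 0.125 × 0.875) + 0.842 × √(0.20 × 0.80 + 0.05 × 0.95)]² / 0.15² = (0.917 + 0.383)² / 0.0225 ≈ 75.1, so 76 per arm.
- With correction: (75.1 / 4) × [1 + √(1 + 4 / (75.1 × 0.15))]² ≈ 87.9, so 88 per arm and 176 in total.

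The stated 176 is reproduced. Nothing in this point changes its inputs.

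**3. How many calls would matter**

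Expected leaks are 88 × 0.20 = 17.6 on placebo and 88 × 0.05 = 4.4 on secretin, about 18 v 4. Two-sided Fisher's exact test with 88 per arm gives:

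| Placebo v secretin | p |
|---|---|
| 18 v 4 (planned rates) | 0.002 |
| 18 v 7 | 0.029 |
| 18 v 8 | 0.054 |
| 13 v 4 | 0.039 |
| 12 v 4 | 0.064 |
| 13 v 5 | 0.079 |
| 11 v 4 | 0.103 |

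In a borderline trial one or two patients move the result across 0.05. At the planned counts it takes four more secretin leaks (18 v 8), or six fewer placebo leaks (12 v 4).

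**4. Effect on type I error under an assumed bias**

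Assume a true leak rate of 20% in both arms, and that a fraction q of true leaks is missed in the secretin arm only. The secretin rate as recorded is then 0.20 × (1 − q). The chance that Fisher's test gives p ≤ 0.05 at 88 per arm is:

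| q | Recorded secretin rate | Probability |
|---|---|---|
| 0 | 20% | 0.032 |
| 5% | 19% | 0.034 |
| 10% | 18% | 0.042 |
| 20% | 16% | 0.074 |
| 30% | 14% | 0.137 |

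The values of q are assumptions; the documents give none. Because Fisher's test is conservative here, the rate stays below 0.05 at q = 10% and exceeds it at q = 20%.

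**The case against.** A single custodian of the code can be a way of keeping everyone else blind, and Sections 4, 14b and 27c can be read in that light. The list in Section 4 describes what the forms will finally contain; given release at discharge, the assignment could be entered only then. Nothing says that the custodian judges leaks. The intra-operative findings, including whether further closure was attempted, come from the attending surgeon, who is blinded. One wording of the primary outcome, and the regression in Section 7b, rest on amylase alone. The form itself is in an appendix that is not in the text reviewed.

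Most of this stands. A reader might infer that the arm is visible to whoever assesses leaks in the operating room and on the ward, so that the double-blind claim has already failed. The documents do not support that: time of entry, who completes the form and the custodian's role are all unstated, and the operating-room observation belongs to a blinded person.

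The objection does not supply the missing safeguard. The custodian's access has no time limit, so late entry on the form would not by itself keep that person blind during the admission. The investigators who generate the list are not said to be kept from it. The ISGPF endpoint in Section 7a retains a clinical judgement. The leak follow-up after discharge falls, on the plan's own timetable, after assignments are revealed.

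**Conclusion.** The concern holds as an unprotected route to bias, not as a demonstrated breach of blinding. Arm and outcomes share the forms, one person holds both, blinding is stated only for surgeon and patient, and no provision keeps a person who knows the arm from completing the form or classifying a leak. The clearest exposure in the text is the leak assessment after discharge.

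Its size cannot be estimated from the documents. A reader might infer from the 11 v 4 and 13 v 4 results that a couple of calls would decide this trial. That is true only of a borderline outcome; at the planned rates p is about 0.002 and several calls would be needed. The conclusion also assumes that the clinical part of the ISGPF definition enters the primary endpoint. If amylase alone decides, there is much less room for judgement. The change should be made because it closes the route at almost no cost.

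**What to change.** - In Section 4, remove the assignment from the items recorded on the forms and identify patients there by study number only.
- Keep the code list with the Investigational Pharmacy named in Section 30, not with the researcher who holds the outcomes. This assumes that the pharmacy manages the study drug; the tick-box answer cannot be read in the text.
- Link assignment to outcome only after each patient's outcome through day 30 has been classified and the database is locked.
- For the interim look in Section 8, give the monitoring board coded arms. The trigger concerns either group and the comparison is two-sided, so neither needs the arms named.
- Reconcile Sections 4, 7b and 14b, and 27c with them: who generates the list, who holds it, who completes the form, who classifies leaks, and when and to whom assignments are released.

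The cost is one data item and a few sentences, with no change to the 176 patients or to any procedure. The release now set at discharge would have to move. The downside is that the data holder cannot check assignments before lock.
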